### 18.5.3. Modified Duke Criteria for Endocarditis

The Modified Duke Criteria for Endocarditis ix may be used to diagnose endocarditis events for the HAMMOCK PAS study, in the absence of reoperation or autopsy.

Criteria	Definite Infective Endocarditis	Possible Infective Endocarditis	Not Infective Endocarditis

 
Pathologic
 
			
Histologic	Vegetation or intracardiac abscess present, confirmed by histology showing active endocarditis	Short of definite, but not rejected	No pathologic evidence of infective endocarditis with antibiotic therapy for 4 days or less

 
Or
 
			
Bacteria	Demonstrated by culture or histology in a vegetation, or in a vegetation that has embolized, or in an intracardiac abscess	Short of definite, but not rejected	No pathologic evidence of infective endocarditis with antibiotic therapy for 4 days or less

 
Clinical - any one of following:
 
			
Major criteria	2 criteria met	Does not apply	
 
Resolution of manifestations of endocarditis, with antibiotic therapy for 4 days or less, or firm alternate diagnosis for manifestations of endocarditis. Does not meet criteria for possible infective endocarditis
 

Minor criteria	5 criteria met	3 criteria met	
Major and minor	1 major + 3 minor	1 major and 1 minor	

Major Criteria
A. Supportive laboratory evidence

 
▪ Typical microorganism for infective endocarditis from two separate blood cultures: viridans streptococci, Staphylococcus aureus, Streptococcus bovis, HACEK group (Haemophilus spp. Actinobacillus actinomycetemcomitans, Cardiobacterium hominis, Eikenella spp., and Kingella kingae) or
 
▪ Community-acquired enterococci, in the absence of a primary focus
 
▪ Persistently positive blood culture, defined as recovery of a microorganism consistent with infective endocarditis from blood cultures drawn more than 12 hours apart or
 
▪ Persistently positive blood culture, defined as recovery of a microorganism consistent with infective endocarditis from all of three or a majority of four or more separate blood cultures, with first and last drawn at least 1 hour apart.
 
▪ Single positive blood culture for Coxiella burnetii or phase I antibody titer >1:800
 

B. Evidence of endocardial involvement
Echocardiogram supportive of infective endocarditis.
1. Type of study

TEE recommended as first test in the following patients: a) prosthetic valve endocarditis; or b) those with at least "possible" endocarditis by clinical criteria; or c) those with suspected complicated endocarditis, such as paravalvular abscess. TTE recommended as first test in all other patients
 
2. Definition of positive findings
 
 
• oscillating intracardiac mass, on valve or supporting structures, or in the path of regurgitant jets, or on implanted material, in the absence of an alternative anatomic explanation or myocardial abscess or new partial dehiscence of prosthetic valve
 
• C. New valvular regurgitation (increase or change in pre-existing murmur not sufficient)
 

Minor Criteria
Predisposing heart condition or intravenous drug use
Fever $\geq 38.0$ C (100.4 F)
Vascular phenomena: major arterial emboli, septic pulmonary infarcts, mycotic aneurysm, intracranial hemorrhage, conjunctival hemorrhage, Janeway lesions
Immunologic phenomena: glomerulonephritis, Osler's nodes, Roth spots, rheumatoid factor

 
• Positive blood culture not meeting major criterion as noted previously (excluding single positive cultures for coagulase-negative staphylococci and organisms that do not cause endocarditis) or serologic evidence of active infection with organism consistent with infective endocarditis
 

#### 18.5.4. Aortic Valve Regurgitation

One of the endpoints for the HAMMOCK PAS is paravalvular leak of the study valve. Severity of any paravalvular leak will be measured using the ASE recommended parameters to assess Aortic Regurgitation (AR) severity x, as outlined in the table below.

Parameter	Mild	Moderate	Severe
Valve structure and motion			
Mechanical or bioprosthetic	Usually normal	Abnormal 	Abnormal 
Structural parameters			
LV size	Normal 	Normal or mildly dilated 	Dilated 
Doppler parameters (qualitative or semi-quantitative)			
Jet width in central jets (% LVOT diameter): color 	Narrow ( $\leq 25\%$ )	Intermediate (26% - 64%)	Large ( $\geq 65\%$ )
Jet density: CW Doppler	Incomplete or faint	Dense	Dense
Jet deceleration rate (PHT, ms): CW Doppler 	Slow ( $> 500$ )	Variable (200 – 500)	Steep ( $< 200$ )
LVOT flow vs pulmonary flow: PW Doppler	Slightly increased	Intermediate	Greatly increased
Diastolic flow reversal in descending aorta: PW Doppler	Absent or brief early diastolic	Intermediate	Prominent, holodiastolic
Circumferential extent of prosthetic paravalvular regurgitation (%)	<10	10 – 19	$\geq 20$
Doppler Parameters (quantitative)			
Regurgitant volume (ml/beat)	<30	30 – 59	$\geq 60$
Regurgitant fraction (%)	<30	30 – 49	$\geq 50$

Notes:

PHT = pressure half-time

 Parameter applicable to central jets, and is less accurate in eccentric jets; Nyquist limit of 50 – 60 cm/sec.

 Abnormal mechanical valves, for example, immobile occluder (valvular regurgitation), dehiscence or rocking (paravalvular regurgitation); abnormal biologic valves, for example, leaflet thickening or prolapse (valvular), dehiscence or rocking (paravalvular regurgitation).

 Applies to chronic, late postoperative AR in the absence of other etiologies.

 Influenced by LV compliance.

Not well validated and may overestimate severity compared with quantitative Doppler

### 18.5.5. Mitral Valve Regurgitation

One of the endpoints for the HAMMOCK PAS is paravalvular leak of the study valve. Severity of any paravalvular leak will be measured using the ASE recommended parameters to assess Aortic Regurgitation (AR) severity xi, as outlined in the table below.

Parameter	Mild	Moderate	Severe
Structural parameters			
LV size	Normal 	Normal or dilated	Usually dilated 
Prosthetic valve 	Usually normal	Abnormal 	Abnormal 
Doppler parameters			
Color flow jet area 	Small, central jet (usually <4 cm  or <20% of LA area)	Variable	Large central jet (usually >8 cm  or >40% of LA area) or variable size wall-impinging jet swirling in left atrium
Flow convergence 	None or minimal	Intermediate	Large
Jet density: CW Doppler 	Incomplete or faint	Dense	Dense
Jet contour: CW Doppler 	Parabolic	Usually parabolic	Early peaking, triangular
Pulmonary venous flow 	Systolic dominance 	Systolic blunting 	Systolic flow reversal 
Quantitative Parameters 			
VC width (cm) 	<0.3	0.3 – 0.59	≥0.6
R vol (mL/beat)	<30	30 – 59	≥60
RF (%)	<30	30 – 49	≥50
EROA (cm  )	<0.20	0.20 – 0.49	≥0.50

Notes:

EROA, Effective regurgitant orifice area; RF, regurgitant fraction; R vol, regurgitant volume; VC, vena contracta.

 LV size applied only to chronic lesions.

 Pulmonary venous systolic flow reversal is specific but not sensitive for severe MR.

 In the absence of other etiologies of LV enlargement and acute MR.

 Unless other reasons for systolic blunting (eg, atrial fibrillation, elevated LA pressure).

 Parameter may be best evaluated or obtained with TEE, particularly in mechanical valves.

 Abnormal mechanical valves, for example, immobile occluder (valvular regurgitation), dehiscence or rocking (paravalvular regurgitation); abnormal biologic valves, for example, leaflet thickening or prolapse (valvular), dehiscence or rocking (paravalvular regurgitation).

 At a Nyquist limit of 50 to 60 cm/s.

 Minimal and large flow convergence defined as a flow convergence radius <0.4 and ≥0.9 cm for central jets, respectively, with a baseline shift at a Nyquist limit of 40 cm/s; cutoffs for eccentric jets may be higher.

 These quantitative parameters are less well validated than in native MR.

## 18.6. Investigational Sites

A listing of the investigational sites, name, address and professional position of PI's and coordinating investigator(s) if assigned) will be provided under separate cover.

### 18.6.1. Site Selection

The following criteria will be used to select investigators and sites for participation:

- Experience in cardiothoracic surgery and surgical aortic and/or mitral valve replacement
- The presence or capacity of establishing an investigative team capable of managing the duties of the clinical trial
- Access to the necessary cardiovascular facilities and services to complete protocol required study procedures and follow-up.
- Availability of the study device(s)
- A sufficient patient population to meet enrollment expectations (estimated treatment of 10 subjects at each site, with a maximum of 20 treated subjects (or 20% of the total trial population)
- Willingness to comply with the requirements described in this CIP

A listing of Investigators and investigative centers/sites will be provided under separate cover.

### 18.6.2. Research Agreement and Financial Disclosure

A Clinical Investigation Agreement shall be signed by the participating investigational site and/or the PI at each investigational site per the local legal requirements, and returned to Medtronic prior to trial activation. The Investigator is required to indicate their approval of the CIP (and any subsequent amendments), by signing and dating the agreement. All Investigators will be asked to complete financial disclosure statements provided by Medtronic prior to their participation in the trial.

### 18.6.3. Training of Investigative Staff

Medtronic will provide training to the investigative team, according to the Training Plan, on the trial Requirements as applicable. Training required per local law/regulation will occur prior to site activation at each site.

Site personnel (including new personnel) must be trained and activated by Medtronic prior to performing any protocol related duties.

### 18.6.4. Site Activation

Investigational sites will receive a formal letter of site activation, upon receipt of or completion of the following:

- Curriculum vitae of the Principal and Sub-investigators and all key site staff
- A signed research agreement
- A signed Investigator statement
- Financial disclosure from the Investigators
- Competent Authority (as applicable to the geography)
- A copy of the IRB/Ethics Board approval letter, along with the voting roster
- The IRB/Ethics Board approved informed consent form

- Documented training of the investigative team
- Delegated Task List
- Lab certificate and lab normal values/ranges

7.6.2.2. Endpoints	10
7.6.2.3. Data Collection and Analysis Methods	10
8. References.....	Error! Bookmark not defined.

1. Version History

Version	Summary of Changes	Author(s)/Title
1.0	
 Not Applicable, New Document 	[name] / Principal Statistician
2.0	
 To align with CIP version 2.0 
 Add wording “valve-related” to death Change word “hemodynamic” to “clinical” Update site information Update inclusion/exclusion Update data collection Update minimizing bias 	[name] / Principal Statistician

2. List of Abbreviations and Definitions of Terms

Abbreviation	Definition
AE	Adverse Event
CIP	Clinical Investigational Plan
SAP	Statistical Analysis Plan

3. Introduction

The Mosaic and Hancock II bioprostheses received CE Mark in 1995, and FDA approval in 2000 and 1999 respectively. The Mosaic and Hancock II have been in the market worldwide for over 20 years. The devices have a safe history of use as indicated by the published clinical data and by the low complaint and adverse event rates collected through product surveillance.

The current stent material used for the bare stent in the Mosaic and Hancock II bioprostheses, acetal homopolymer (AHP), has been discontinued by the supplier. Medtronic completed a formal material selection process to evaluate replacement materials and selected polyether ether ketone (PEEK) as the optimal replacement material for the stent. As part of the pre-clinical qualification for the substitution of acetal homopolymer (AHP) with Polyetheretherketone (PEEK) material in Mosaic and Hancock II valve stents, Medtronic completed a thorough analysis to identify potential risks associated with the material change. Design verification testing demonstrated equivalent functional performance and non-inferior structural performance and durability of the PEEK stented valves versus the prior stented valve with AHP stent material.

The purpose of the study is to complete a prior agreed upon requirement for the continuation of CE Mark by providing the Notified Body with supplemental post market clinical follow-up data on the safety and performance of the Mosaic and Hancock II devices with PEEK material at 1 year post implant for the primary endpoint with a pre-determined and agreed upon study follow-up duration of 3 years post treatment. This Statistical Analysis Plan (SAP) is designed to document, before data are analyzed, the rationale for the study design of the Medtronic HAMMOCK PAS Study, and the planned analyses that will be included in study reports. The design and analyses are consistent with the objectives of the Clinical Investigational Plan (CIP).

This Statistical Analysis Plan (SAP) applies to the publications and the final study report. The publications may request additional analyses that are not included in this SAP.

4. Study Objectives

4.1. Primary Objective(s)

The primary objective of the study is to characterize the freedom from valve related death, re-intervention of, or explant related to the Mosaic and Hancock II valves with PEEK stent material in a patient population undergoing aortic or mitral valve replacement of his/her native aortic or mitral valve at 1 year post implant.

4.2. Secondary Objective(s)

The secondary objective of the study is to characterize the clinical performance of Mosaic and Hancock II valves containing PEEK stent material at 1 year post implant.

5. Investigation Plan

This is a prospective, interventional, non-randomized, worldwide, multi-center study, with each site following a single common protocol. The design of the study adheres to the principles of International Conference on Harmonization Guidelines on Good Clinical Practice (GCP), Declaration of Helsinki and ISO 14155:2011.

The study will be conducted at up to 15 sites worldwide with approximately up to 7 sites in the US and up to 8 sites in Europe with a maximum of 110 total subjects enrolled and a minimum of 100 study subjects implanted. Enrolled subjects who exit the study will not be replaced. Subjects eligible for aortic or mitral valve replacement and compliant with the enrollment criteria will be considered by the investigator for inclusion in the study.

Adverse Events collection is limited to all Serious Adverse Events, all device and procedure related Adverse Events and all Device Deficiencies.

Enrollment is estimated to take approximately 15 months to complete and subjects will consent to be followed annually up to 3 years post procedure. A minimum of 89 subjects is required to be followed to 1-year to satisfy the primary endpoint requirements: freedom from valve related death, re-intervention of, or explant study valve related to the Mosaic and Hancock II valves with PEEK stent material. Total expected duration of the study is approximately 5 years. The study will be considered complete when the last active implanted subject completes the 3 year required follow-up.

Sponsor shall avoid improper influence on, or inducement of, the subject, monitor, any investigator(s) or other parties participating in, or contributing to, the clinical study. Selection of subjects, treatment of subjects and evaluation of study data are potential sources of bias.

Methods incorporated in the study design to minimize potential bias include (but are not limited to):

- For sites that are participating in other Aortic or Mitral valve studies which may have similar enrollment criteria as the HAMMOCK PAS Study, a written process for avoiding selection bias is strongly recommended
- Demographics and medical history will be collected at baseline in order to later assess possible characteristics that may influence endpoints

- Data collection requirements and study procedures will be standardized across all geographies
- All geographies will follow the same version of the CIP and eCRFs
- No more than 20% of expected implants may come from a single site
- All study investigators will be required to meet the requirements of 21 CFR Part 54, Financial Disclosure by Clinical Investigators
- All study site and Medtronic personnel will be trained using standardized training materials
- Study sites should follow their institutional procedures for maintenance of echocardiography and laboratory equipment used for assessing the study variables. Regular monitoring visits will be conducted to verify adherence to the CIP and source data
- An independent Clinical Events Committee (CEC) will be utilized to regularly review and adjudicate reported endpoint related adverse events

Subjects must meet all of the following criteria to be included in the study.

1. Subjects who require aortic or mitral valve replacement of his/her native a Mosaic or Hancock II bioprostheses with PEEK Material.
2. Subject is geographically stable and willing to return to the implanting site for all follow-up visits.
3. Subject is of legal age to provide informed consent in the country where they enroll in the study.
4. Subject has been adequately informed of risks and requirements of the study and is willing and able to provide informed consent for participation in the clinical study.

Subjects who meet any of the following criteria will not qualify for participation in the study.

1. Subject requires concomitant replacement of the aortic and mitral valves.
2. Subject requires a replacement of a previously implanted failed prosthetic aortic or mitral valve.
3. Subject requires a Bentall procedure for replacement of aortic valve or aortic root.
4. Subject presents with active endocarditis, active myocarditis, or other active systemic infection.
5. Subject has a non-cardiac major or progressive disease, with a life expectancy of less than 1 year. These conditions include, but are not limited to:
 - a. Child-Pugh Class C liver disease
 - b. Terminal cancer
 - c. End-stage lung disease
6. Subject has chronic renal failure, defined as dialysis therapy or GFR<30 mL/min/1.73 m².
7. Subject has hyperparathyroidism.
8. Subject is participating in another investigational device or drug study or observational competitive study.
9. Subject is pregnant, lactating, or planning to become pregnant during the study period.
10. Subject has systolic EF<20% as assessed by echocardiography.
11. Subject has Grade IV Diastolic Dysfunction.
12. Subject requires emergency surgery.
13. Subject is less than legal age of consent, legally incompetent, or otherwise vulnerable such that subject cannot provide informed consent.

6. Determination of Sample Size

PASS (2013) software was used to calculate the sample size. Confidence interval method for one proportion was utilized. When the sample event free proportion assumed to be 97% at 1 year post implantation, to achieve a one-sided 95% confidence interval width of 5.0% or less, a sample size of 89 subjects with the exact (Clopper-Pearson) confidence interval method for one proportion. Allowing for attrition rate of up to 20% in the first year, a total of up to 110 subjects will be enrolled.

7. Statistical Methods

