	
9. Subject is pregnant, lactating, or planning to become pregnant during the study period.
 
10. Subject has systolic EF<20% as assessed by echocardiography.
 
11. Subject has Grade IV Diastolic Dysfunction.
 
12. Subject requires emergency surgery.
 
13. Subject is less than legal age of consent, legally incompetent, or otherwise vulnerable such that subject cannot provide informed consent.

Study Procedures and Assessments	Data will be collected for subjects meeting the eligibility criteria preoperatively, at discharge or ≤ 30 days post-implant (whichever comes first), 1 year (primary endpoint), 2 years, and 3 years post-operatively.
Safety Assessments	Data will be collected on all Serious Adverse Events, all device and procedure related Adverse Events and all Device Deficiencies. All valve related deaths and potential primary safety endpoint events will be assessed by an independent clinical events committee review. Adverse events and device deficiencies need to be reported on eCRFs per the reporting requirements for this study and on specific country requirements per local law.
Statistics	
In order to characterize the freedom from valve related deaths, re-intervention of, or explants related to the Mosaic or Hancock II valve containing PEEK stent material at 1 year the following statistical method will be used:
 
A sample size of 89 at 1-year will provide a one-sided 95% confidence interval width of 5%, when the sample event free proportion assumed to be 97% at 1 year post implant. Considering the attrition rate of 10% per year, a minimum of 100 subjects will be enrolled and treated.
 
A survival analysis, using Kaplan-Meier method will estimate the 1-year event free probability (valve related deaths, re-intervention of, or explant related to the Mosaic and Hancock II valves with PEEK stent material) using a 1-sided lower 95% CI to evaluate. All subjects will be followed and evaluated up to 3 years.

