## 7. Study Design

This is a prospective, interventional, non-randomized, worldwide, multi-center study, with each site following a single common protocol. The design of the study adheres to the principles of International Conference on Harmonization Guidelines on Good Clinical Practice (GCP), Declaration of Helsinki and ISO 14155:2011.

Regarding Adverse Event collection the study is deviating from ISO 14155:2011 as Adverse Events collection is limited to all Serious Adverse Events, all device and procedure related Adverse Events and all Device Deficiencies.

The study will be conducted at up to 15 sites worldwide with approximately up to 7 sites in the US and up to 8 sites in Europe with up to 110 total subjects implanted and a minimum of 100 study subjects implanted. Enrolled subjects who do not receive the study device and exit the study may be replaced in the study as long as the replacement does not exceed the 22 subject implants at the site or the 110 total subject maximum. Subjects eligible for aortic or mitral valve replacement and compliant with the enrollment criteria will be considered by the Investigator for inclusion in the study.

Enrollment parameters are included in the study to avoid introduction of bias to the study results due to disproportionate enrollment. Per site there is no minimum implant requirement; however, a maximum of 22 implanted subjects per site (or 20% of the total implanted population) will be allowed.

Sponsor shall avoid improper influence on, or inducement of, the subject, monitor, any investigator(s) or other parties participating in, or contributing to, the clinical study.

Selection of subjects, treatment of subjects and evaluation of study data are potential sources of bias. Methods incorporated in the study design to minimize potential bias include (but are not limited to):

- For sites that are participating in other Aortic or Mitral valve studies which may have similar enrollment criteria as the HAMMOCK PAS study, a written process for avoiding selection bias is strongly recommended
- Demographics and medical history will be collected at baseline in order to later assess possible characteristics that may influence endpoints
- Data collection requirements and study procedures will be standardized across all geographies
- All geographies will follow the same version of the CIP and eCRFs
- No more than 20% of expected implants may come from a single site

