## 7.1. Duration

Enrollment is estimated to take approximately 15 months to complete, and subjects will consent to be followed annually up to 3 years post procedure. A minimum of 89 subjects is required to be followed to 1 year to satisfy the primary endpoint requirements: freedom from valve related death, re-intervention of, or explant related to the Mosaic and Hancock II valves with PEEK stent material. Total expected duration of the study is approximately 5 years. The study will be considered complete when the last active implanted subject completes the 3 year required follow-up.

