### 14.2.2. Sample Size

A sample size of 89 at 1 year will provide a one-sided 95% confidence interval width of 5%, when the sample event free proportion assumed to be 97% at 1 year post implant. Considering the possible attrition rate assumed to be  $\leq 10\%$  in the first year, a minimum of 100 subjects will be implanted.

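### The SAP allows up to 20% first-year attrition and the protocol 10%; 100 implants leave the required 89 at 1 year only at 11% or less, and the 110 cap and replacement rule differ.

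*SAP*

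**What the plan says.** **Attrition.** After deriving 89 evaluable subjects, SAP section 6 states: "Allowing for attrition rate of up to 20% in the first year, a total of up to 110 subjects will be enrolled". The protocol synopsis (section 4) states: "Considering the attrition rate of 10% per year, a minimum of 100 subjects will be enrolled and treated". Protocol section 14.2.2 assumes attrition of at most 10% "in the first year, a minimum of 100 subjects will be implanted".

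**Required count.** Protocol section 7.1: "A minimum of 89 subjects is required to be followed to 1 year to satisfy the primary endpoint requirements". SAP section 5 agrees: "A minimum of 89 subjects is required to be followed to 1-year".

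**Cap and replacement.** SAP section 5 describes a study "with a maximum of 110 total subjects enrolled and a minimum of 100 study subjects implanted", and adds: "Enrolled subjects who exit the study will not be replaced". Protocol section 7 describes one "with up to 110 total subjects implanted and a minimum of 100 study subjects implanted". Protocol sections 7 and 10.10 let enrolled subjects who do not receive the device be replaced, within the site and overall limits.

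**Site limit.** This is 20 enrolled in SAP section 7.3, 22 implanted in protocol sections 7 and 10.10, and 20 treated in protocol section 18.6.1.

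**Versions.** The SAP's version history aligns it to protocol version 2.0. The protocol is now at version 3.0, and its history records a change to the enrolled and implanted maxima.

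**The concern.** The two documents start from the same 89 and inflate it with first-year loss rates that differ by a factor of two. They also attach the rate to different bases: enrolled subjects in SAP section 6, implanted subjects in protocol section 14.2.2. Yet they share one minimum of 100 implants, which can be matched to only one of the two rates.

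The cap and replacement rules compound this. Enrollment is the signing of consent (protocol section 9.2), so consented subjects who never receive a valve use up places under the SAP's rule but not under the protocol's.

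At stake is the count of 89 that both documents call necessary for the primary endpoint, in a study run as a condition of CE mark. Whether the planned numbers deliver it depends on which document is read.

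**Working it through.** **Inputs.** Event-free proportion 97%, one-sided 95% exact (Clopper-Pearson) limit, target width 5.0% or less (SAP section 6); 89 at 1 year, minimum 100 implanted, cap 110 (both documents); attrition up to 20% (SAP section 6) or 10% (protocol sections 4 and 14.2.2).

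**1. Reproduce the 89.** The lower limit L is the 5th percentile of Beta(x, n − x + 1) with x = 0.97n, and the width is 0.97 − L.

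| n | L | Width |
|---|---|---|
| 80 | 0.9163 | 5.37% |
| 88 | 0.9199 | 5.01% |
| 89 | 0.9203 | 4.97% |
| 90 | 0.9207 | 4.93% |

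The smallest n with width at most 5.0% is 89, as stated.

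**2. Inflate for attrition: n / (1 − d).**
- 10%: 89 / 0.90 = 98.9, so 99. The protocol's 100 covers it.
- 20%: 89 / 0.80 = 111.25, so 112. The SAP's 110 is two short, which is rounding-level. The 100 minimum is twelve short.

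**3. Completers from the planned numbers.**

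| Implanted | 10% loss | 20% loss | Highest loss leaving 89 |
|---|---|---|---|
| 100 | 90 | 80 | 1 − 89/100 = 11.0% |
| 110 | 99 | 88 | 1 − 89/110 = 19.1% |

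**4. Does a different base reconcile the rates?** If the SAP's 20% covered all loss from consent, then 110 enrolled, 100 implanted and 90 at 1 year is 1 − 90/110 = 18.2%, and the documents would agree. The SAP does not say this. It calls the 20% first-year attrition, and SAP section 7.1.1 sets time zero at the procedure.

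**5. Cap and replacement.** Under the SAP, 110 − 100 = 10 consented subjects may go without an implant. The eleventh makes the 100 minimum unreachable. Under the protocol's rule it does not.

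**6. Expected width under the planned analysis.** SAP section 7.6.1.3 uses Kaplan-Meier with a log-log limit, which keeps the time at risk of subjects who are lost. Assume a constant event hazard λ = −ln 0.97, and let G(t) be the proportion not yet lost at time t (in years):

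- Greenwood sum V = ∫₀¹ λ / [N·G(t)·S(t)] dt
- Lower limit = 0.97^exp(1.645·√V / |ln 0.97|)

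For N = 100 and even loss, G(t) = 1 − 0.2t. Then V = 0.000345, √V / |ln 0.97| = 0.610, and the lower limit is 0.9203, a width of 4.97%. This equals the precision of about 89.6 subjects without loss.

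| 20% loss, timing | 100 implanted | 110 implanted |
|---|---|---|
| All at year end | 4.57% | 4.26% |
| Even over the year | 4.97% | 4.62% |
| All at day 0 | 5.43% | 5.04% |

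At 100 implanted, the width stays at or below 5.0% up to about 21% attrition if loss is even, and up to about 11% if all loss is at day 0.

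**The case against.** **Each document's own chain nearly works.** The protocol pairs 10% with 100, and the SAP pairs 20% with 110; only the second misses, by one completer. The figure of 80 puts the SAP's loss ceiling on the implant floor, a worst case on a worst case. This is fair as to likelihood. But SAP sections 5 and 6 themselves contain the 100 minimum, the 20% allowance and the required 89, so the combination lies within one document.

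**The rates need not conflict.** An allowance of up to 20% and an assumption of at most 10% can both be true, and counting loss from consent brings the totals into line. That is plausible, but the SAP does not state it and its first-year wording points the other way.

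**The planned analysis absorbs most of the loss.** This stands. The completer-only widths of 5.01% and 5.37% do not describe the Kaplan-Meier analysis, which holds about 5% at 100 implanted unless losses come early. Neither document states a consequence of falling below 89.

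**The cap mismatch is version lag.** This largely stands as an explanation, but the SAP text in force still contradicts the protocol in force.

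**The site cap is a separate matter.** Agreed. It does not bear on attrition. A common 20% rule gives 22 of 110 or 20 of 100, which accounts for the two numbers but not for the different bases (enrolled, implanted, treated). Version lag cannot explain it, because the protocol differs from itself.

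**Conclusion.** The concern holds. The derivation of 89 is correct, and the protocol's 100 follows from 10% attrition. The SAP's 20% allowance does not deliver the required 89 if it applies to implanted subjects: 88 from 110, which is trivial, and 80 from the 100 minimum, which is nine short. The SAP's cap and replacement rules also contradict the current protocol.

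The consequence is limited to the follow-up count and the stated precision. With no hypothesis or success threshold, no power figure or decision changes. The Kaplan-Meier widths rest on 97% event-free, a constant event hazard and the stated loss patterns. The shortfall in count rests on reading the 20% as loss after implant, which is the natural reading of the SAP but not an explicit one. This should be corrected, but it does not threaten the design.

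**What to change.** No added patients are needed.

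1. State one first-year attrition rate, and whether its base is enrolled or implanted subjects, in SAP section 6 and protocol sections 4 and 14.2.2. If loss from consent was meant, say so and show 110 enrolled, 100 implanted, 90 at 1 year.
2. Bring SAP sections 5, 6 and 7.3 into line with protocol version 3.0: a cap on implanted subjects, and replacement of those who do not receive the device. This replacement does not offset losses after implant.
3. If 20% is kept, give the worst-case counts and widths (110 leaves 88, 5.01%; 100 leaves 80, 5.4%), label them completer-only, and add the expected Kaplan-Meier width with its range.
4. Separately, settle the site cap and its base across SAP section 7.3 and protocol sections 7, 10.10 and 18.6.1. Aligning the SAP to the protocol will not do this alone.

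The cost is wording in the SAP and a few lines in the protocol, and a stated worst-case precision slightly less favourable than 5.0%.
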